6.4. Study Intervention Compliance

Participants will receive study intervention directly from the investigator or designee, under medical supervision. The date and administrations time of each injection will be recorded in the source documents. The dose of study intervention and study participant identification will be confirmed at the time of dosing by a member of the study site staff other than the person administering the study intervention.

6.5. Dose Modification

Dose modifications are not applicable for this study. See Section [7.1](#) for instructions to discontinue study intervention for safety reasons.

6.6. Continued Access to Study Intervention after the End of the Study

There will not be continued access to study intervention after the end of the study.

6.7. Treatment of Overdose

For this study, any dose of sotrovimab greater than the protocol-defined dose and frequency (one-time dose) will be considered an overdose.

No specific treatment is recommended for an overdose. The treating physician may provide supportive measures depending on the symptoms.

In the event of an overdose, the treating physician should:

1. Contact the medical monitor immediately.
2. Closely monitor the participant for AE/SAE and laboratory abnormalities.
3. Document the quantity of the excess dose as well as the duration of the overdosing in the CRF.

Decisions regarding dose interruptions or modifications will be made by the investigator in consultation with the Medical Monitor based on the clinical evaluation of the participant.

6.8. Concomitant Therapy

Any medication or vaccine (including over-the-counter or prescription medicines, recreational drugs, vitamins, and/or herbal supplements) that the participant is receiving at the time of enrollment or receives during the study must be recorded along with:

- reason for use
- dates of administration including start and end dates

- dosage information including dose and frequency

The medical monitor should be contacted if there are any questions regarding concomitant or prior therapy.

Receipt of any investigational (not authorized or approved) SARS-CoV-2 vaccine is not permitted during the study. Receipt of any authorized or approved SARS-CoV-2 vaccine is not permitted following 90 days post-dosing per CDC guidelines (<https://www.cdc.gov/vaccines/covid-19/info-by-product/clinical-considerations.html>). Participants should consult with the primary investigator and their primary care physician on local guidelines for vaccine administration and guidance on the risks associated with administration of all vaccines while on study.

Participants must abstain from taking prescription or non-prescription drugs (including vitamins, recreational drugs, and dietary or herbal supplements) within 7 days (or 14 days if the drug is a potential enzyme inducer) or 5 half-lives (whichever is longer) before the start of study intervention until completion of the follow-up visit, unless, in the opinion of the investigator and Medical Monitor, the medication will not interfere with the study.

Paracetamol/acetaminophen, at doses of ≤ 2 g/day, is permitted for use any time during the study. Other concomitant medications may be considered on a case-by-case basis by the investigator in consultation with the medical monitor if required.

Pharmaceutical methods of contraception as described in Section 10.4.2 are permitted for use at any time during the study.

All prior and concomitant medication should be captured in the eCRF.

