5.2. Exclusion Criteria

Participants are excluded from the study if any of the following criteria apply:

Medical Conditions

- 1. History or presence of cardiovascular, respiratory, hepatic, renal, gastrointestinal, endocrine, hematological, or neurological disorders capable of significantly altering the absorption, metabolism, or elimination of drugs; constituting a risk when taking the study intervention or interfering with the interpretation of data.
- 2. Abnormal BP as defined as greater than 140 mm/Hg systolic, greater than 90 mm/Hg diastolic, or less than 90 mm/Hg systolic at Screening. BP at Screening is the average of 3 BP readings taken using the methods described in Section [8.3.2](#).
- 3. Known hypersensitivity to any constituent present in the investigational product or history of severe hypersensitivity or anaphylaxis after receiving a COVID-19 vaccine.
- 4. Clinically significant multiple or severe drug allergies, intolerance to topical corticosteroids, or severe post-treatment HSRs (including, but not limited to, erythema multiforme major, linear immunoglobulin A [IgA] dermatosis, toxic epidermal necrolysis, and exfoliative dermatitis).

5. Lymphoma, leukemia, or any malignancy within the past 5 years except for basal cell or squamous epithelial carcinomas of the skin that have been resected with no evidence of metastatic disease for 3 years.
6. For Part A and Part B, any condition that would prohibit receipt of IM injections in the investigator's opinion, such as coagulation disorder, bleeding diathesis, or thrombocytopenia.
7. Breast cancer within the past 10 years.
8. Alanine aminotransferase (ALT) $>1.5 \times$ upper limit of normal (ULN).
9. Total bilirubin $>1.5 \times$ ULN (isolated total bilirubin $>1.5 \times$ ULN is acceptable if total bilirubin is fractionated and direct bilirubin $<35\%$).
10. Current or chronic history of liver disease or known hepatic or biliary abnormalities (with the exception of Gilbert's syndrome or asymptomatic gallstones).
11. Participants exposed to an individual known to be infected with COVID-19 by PCR testing within the 14 days prior to Screening.
12. QT interval corrected using Fridericia's formula (QTcF) >450 msec.

Prior/Concomitant Therapy

13. Use of any over-the-counter or prescription medications within 7 days (or 14 days if the drug is a potential enzyme inducer) or 5 half-lives (whichever is longer) prior to dosing until completion of the follow-up visit, unless permitted in Section 6.8.

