14. Treatment with biologic agents (such as mAbs including marketed drugs) within 3 months or 5 half-lives (whichever is longer) prior to dosing.
15. Receipt of convalescent plasma from a recovered COVID-19 patient or anti-SARS-CoV-2 mAb within the last 3 months.
16. Receipt of any vaccine within 48 hours prior to enrollment.
17. Has received a SARS-CoV-2 vaccine but has not completed all doses in the series more than 28 days prior to Screening. SARS-CoV-2 vaccinations will not be allowed for 90 days after dosing.

Prior/Concurrent Clinical Study Experience

18. Participation in the study would result in loss of blood or blood products in excess of 500 mL within a 56-day period.
19. Exposure to more than 4 new chemical entities (e.g., investigational pharmaceuticals) within 12 months prior to the first dosing day.
20. Enrollment in any investigational vaccine study within the last 180 days or enrollment in any other investigational drug study within 30 days prior to Day 1 or within 5 half-lives of the investigational compound, whichever is longer.
21. Current enrollment or past participation in this clinical study.

Diagnostic Assessments

22. Presence of hepatitis B surface antigen (HBsAg) at Screening or within 3 months prior to first dose of study intervention.
23. Positive hepatitis C antibody test result at Screening or within 3 months prior to first dose of study intervention. NOTE: Participants with positive hepatitis C antibody due to prior resolved disease can be enrolled only if a confirmatory negative hepatitis C ribonucleic acid (RNA) test is obtained.
24. Positive hepatitis C RNA test result at Screening or within 3 months prior to first dose of study intervention. NOTE: Test is optional and participants with negative hepatitis C antibody test are not required to also undergo hepatitis C RNA testing.
25. Positive pre-study drug/alcohol screen.
26. Positive HIV antibody test.

Other Exclusions

27. History of regular alcohol consumption within 6 months prior to the study defined as:
 - An average weekly intake of >14 units. One unit is equivalent to 8 g of alcohol: a half-pint (~240 mL) of beer, 1 glass (125 mL) of wine or 1 (25 mL) measure of spirits.
28. Regular use of known drugs of abuse.
29. Sensitivity to any of the study interventions, or components thereof, or drug or other allergy that, in the opinion of the investigator or medical monitor, contraindicates participation in the study.

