8.4.7.1. Injection-Related Reactions and Serious Hypersensitivity

Guidelines for monitoring relevant AEs encompassing hypersensitivity, angioedema and anaphylaxis as well as for the management of acute anaphylactic shock and minor allergic episodes will be in place at investigational sites. Investigators will be provided with general guidance on management of serious HSRs and such reactions will be managed appropriately per local guidelines/medical judgment. Pre-medications will be permitted at the investigator's discretion and will be appropriately documented.

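### Protocol 6.8 and exclusion 17 place the 90-day bar on authorised SARS-CoV-2 vaccines in opposite windows; read together they bar them for all post-dose follow-up

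*Protocol*

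**What the plan says.** Two places in the protocol set a time rule for SARS-CoV-2 vaccination after dosing.

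- Section 5.2, exclusion 17: "SARS-CoV-2 vaccinations will not be allowed for 90 days after dosing". This sits in a list introduced by "Participants are excluded from the study if any of the following criteria apply", although the sentence governs conduct after dosing and not eligibility.
- Section 6.8, Concomitant Therapy: "Receipt of any authorized or approved SARS-CoV-2 vaccine is not permitted following 90 days post-dosing per CDC guidelines".

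Section 6.8 treats investigational vaccines separately: "Receipt of any investigational (not authorized or approved) SARS-CoV-2 vaccine is not permitted during the study". It then tells participants to consult the investigator and their own physician about local vaccination guidelines and "guidance on the risks associated with administration of all vaccines while on study". Vaccines received during the study are to be recorded with "dates of administration including start and end dates".

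Inclusion criterion 2 (Section 5.1) requires a completed SARS-CoV-2 vaccine series at consent and permits boosters without requiring them. The readable SAP text gives no rule on vaccine timing.

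**The concern.** The two 90-day sentences point in opposite directions. Exclusion 17 closes the first 90 days after dosing and leaves the rest open. Section 6.8, taken at its word, contains no specific bar on authorised SARS-CoV-2 vaccines in the first 90 days and closes everything after them. No other text in either document reconciles the two.

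Section 6.8 is where site staff would look for a vaccination rule during follow-up. Section 8 allows no waivers, so a cautious site may apply both sentences and advise participants against a booster until Week 35, which exclusion 17 plainly does not intend. These are healthy volunteers, and Section 2.3.3 describes any protection they may get from sotrovimab as unproven. Withholding boosters from them through a wording error is worth avoiding.

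The second consequence is for record-keeping. A vaccination that is a deviation under one sentence is not one under the other, so sites could classify the same event differently.

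**Working it through.** No sample size, power or error-rate figure is involved. The check sets the two rules against the follow-up calendar.

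**Inputs**
- Week 35 contact: Day 245 ± 7 days (SAP Section 6.3, Schedule of Activities).
- Dosing is on Day 1, so days after dosing = study day − 1.
- Bar under exclusion 17: days 1 to 90 after dosing.
- Bar under Section 6.8, read literally: day 91 after dosing onward.

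**Length of follow-up**
- Nominal: 245 − 1 = 244 days after dosing.
- Visit window: 238 − 1 = 237 to 252 − 1 = 251 days.

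**Days on which an authorised vaccine is not barred**

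| Rule applied | Days not barred | Share of 244 |
|---|---|---|
| Exclusion 17 alone | 244 − 90 = 154 (147 to 161) | 154/244 = 63.1% |
| Section 6.8 alone, literal | 90 | 90/244 = 36.9% |
| Both | 0 | 0% |

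The two bars do not overlap, and together they cover the whole period: 90 + 154 = 244. Counting follow-up as 35 × 7 = 245 days gives 155 open days under exclusion 17 (155/245 = 63.3%) and still none under both rules.

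**Which vaccinations count as deviations**

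| Vaccine given | Exclusion 17 | Section 6.8, literal |
|---|---|---|
| 20 days after dosing | breach | no breach |
| 120 days after dosing | no breach | breach |

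**Which wording is the likely error.** Three features point to Section 6.8. Both sentences use the same 90-day period. Section 6.8 reserves a whole-study bar for investigational vaccines, and that distinction disappears if authorised vaccines are barred throughout as well. The advice to consult about vaccines while on study would have little purpose for SARS-CoV-2 vaccines under a complete bar. The sentence makes sense if the bar was meant to run for the 90 days after dosing.

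**The case against.** The strongest reply is that nobody would apply Section 6.8 literally. The rest of its own paragraph conflicts with that reading, exclusion 17 states the intended rule clearly, and a site cannot enrol anyone without working through the exclusion list. Section 6.8 also tells sites to contact the medical monitor with any question about concomitant therapy. The affected group is narrow: exclusion 17 requires the vaccine series to be complete more than 28 days before Screening, so only boosters are at issue. On deviations, SAP Section 6.1.3 summarises only those judged important, and nothing says vaccine timing would be.

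Much of this stands. It makes a site relying on Section 6.8 alone unlikely, and it limits the practical effect. It does not remove the contradiction. The sentence is current, operative text; its plain meaning is the reverse of exclusion 17; and the query route helps only a site that notices the conflict.

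A reader might also infer that boosters are barred for the entire study. That goes too far. Both rules start at dosing, and before dosing exclusion 16 bars vaccines only within 48 hours of enrolment.

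**Conclusion.** The inconsistency is real and minor. Taken together, the two sentences leave 0 of about 244 post-dose days open for an authorised SARS-CoV-2 vaccine, against 154 under exclusion 17 alone. They also classify early and late vaccinations in opposite ways.

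The mismatch itself is certain from the text. The intended direction is inferred from exclusion 17 and the context in Section 6.8; the CDC guidance that Section 6.8 cites was not available to confirm it. How sites actually read the sentence is unknown.

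A reader might go further and infer that vaccine reactions could distort the Day 29 adverse-event results, since Day 29 is only 28 days after dosing and falls wholly within the period that Section 6.8 leaves unaddressed. The documents do not support that. Exclusion 17 covers those days. Section 9.3.2 frames the primary objectives regardless of prohibited medication, vaccination dates are recorded, and Section 10.3.3 requires investigators to consider concomitant therapy as an alternative cause. No rate of on-study vaccination is given from which an effect could be estimated. Nor do the documents show any effect on the primary pharmacokinetic comparison. This is a matter of study conduct and not of analysis.

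**What to change.** Reword the sentence in Section 6.8 so that authorised or approved SARS-CoV-2 vaccines are *not permitted for 90 days following dosing*, matching exclusion 17, and send sites a short note stating that this is the rule.

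The cost is one sentence, the usual handling of a protocol amendment and the note. No new data or analysis is needed, and the SAP stays as it is. The one downside is that reactions to vaccines given after 90 days would count in the Week 35 adverse-event incidence, but exclusion 17 already implies this.

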7. DISCONTINUATION OF STUDY INTERVENTION AND PARTICIPANT DISCONTINUATION/WITHDRAWAL

Discontinuation of specific sites or of the study as a whole are detailed in Section 10.1.9.

7.1. Discontinuation of Study Intervention

A participant will be permanently discontinued from completion of drug infusion/injection if they experience a Grade 3 or higher systemic reaction (see Section 10.3 for AE grading).

If treatment intervention is permanently discontinued after a partial dose is received, the participant will remain in the study to be evaluated for follow-up safety assessments as indicated in the SoA (Section 1.3).

7.1.1. Liver Chemistry Stopping Criteria

Liver chemistry stopping, and increased monitoring criteria have been designed to assure participant safety and evaluate liver event etiology. As this is a single-dose study, liver chemistry stopping criteria for a single participant are not applicable. Liver chemistry increased monitoring criteria will apply if participant's ALT is $\geq 3 \times$ ULN and

are described in Section 10.5. Potential Hy's Law case (ALT \geq 3xULN AND total bilirubin \geq 2xULN ($>35\%$ direct bilirubin) or INR >1.5) must be reported as SAE.

7.1.2. **Temporary Discontinuation**

For Part A and Part B: If a participant experiences a Grade 2 systemic reaction after the first injection, investigators will be instructed to pause prior to the second injection. A subsequent injection may be administered at the investigator's discretion, and/or after symptomatic treatment (e.g., antihistamines, IV fluids).

For Part C: A participant will be temporarily discontinued from completion of drug infusion if they experience a Grade 2 (moderate) IRR, investigators will be instructed to pause the infusion. The infusion may subsequently resume at a slower pace at the investigator's discretion, and/or after symptomatic treatment (e.g., antihistamines, IV fluids).

7.2. **Participant Discontinuation/Withdrawal from the Study**

- A participant may withdraw from the study at any time at his/her own request or may be withdrawn at any time at the discretion of the investigator for safety, behavioral, or compliance reasons. This is expected to be uncommon.
- At the time of discontinuing from the study, if possible, an early discontinuation visit should be conducted, as shown in the SoA (Section 1.3). See SoA for data to be collected at the time of study discontinuation and follow-up and for any further evaluations that need to be completed.
- The participant will be permanently discontinued from the study intervention and the study at that time.
- If the participant withdraws consent for disclosure of future information, the sponsor/designee may retain and continue to use any data collected before such a withdrawal of consent.
- If a participant withdraws from the study, he/she may request destruction of any samples taken and not tested, and the investigator must document this in the site study records.

7.3. **Lost to Follow-up**

A participant will be considered lost to follow-up if he/she repeatedly fails to return for scheduled visits and is unable to be contacted by the study site.

The following actions must be taken if a participant fails to return to the clinic for a required study visit:

- The site must attempt to contact the participant and reschedule the missed visit as soon as possible, counsel the participant on the importance of maintaining the assigned visit schedule and ascertain whether the participant wishes to and/or should continue in the study.

- Before a participant is deemed lost to follow-up, the investigator or designee must make every effort to regain contact with the participant (where possible, 3 telephone calls and, if necessary, a certified letter to the participant's last known mailing address or local equivalent methods). These contact attempts should be documented in the participant's medical record.
- Should the participant continue to be unreachable, he/she will be considered to have withdrawn from the study.

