	PIN_TS3.0 ⁷			X	X	X	X	X						10. Hematology assessments will be performed only on Days -1, 2, 5, 8, and 29.
	Pain-NRS ⁸			X	X	X	X	X						11. Screening and Day -1 tests must be >24 hours apart.
	Safety laboratory assessments (hematology ¹⁰ , clinical chemistry, coagulation)	X	X ⁹	X		X	X		X	X	X		X	12. Urine or serum pregnancy test, as per local guidelines. See Section 8.3.5.
Sample collection	Urinalysis and urine albumin to creatinine ratio	X	X				X	X	X	X			X	13. Day 1 sample collection will occur pre-dose, and at 1, 2, 6, 8, 24 (Day 2), and 48 (Day 3) hours after the first injection. On other days, samples will be collected once at any time during the day.
	Urine drug/alcohol screening	X		X										
	HIV, Hepatitis B and C screening	X												
	SARS-CoV-2 molecular test ¹¹	X	X											
	Pregnancy test ¹²	X	X										X	
	Blood sample for PK analysis ¹³			X ¹³	X	X	X	X	X	X	X	X		
	Blood sample for immunogenicity testing (ADA and drug-neutralizing antibody)			X ¹⁴					X		X	X	X	
CCI														
AE review														
SAE review	X ¹⁵	X ¹⁵												

AESI and concomitant medication review		<===== X =====>	
14. On Day 1, sample collection will occur pre-dose.15. At Screening and on Day -1, only SAEs related to study participation or a GSK product will be reported.16. If participant withdraws early from the study prior to Week 24, then the W24 visit assessments will be performed as the ED/EW visit. If the participant withdraws early from the study after Week 24, the W35 visit assessments will be performed as the EW visit.
----------------------------------------	--	-----------------	---------------------------------------------------------------------------------------------------------------------------------------------------------------------------------------------------------------------------------------------------------------------------------------------------------------------------------------------------------------------------------------------------------------------------------------------------------------------------------------------------------

Table 2 Schedule of Activities: Part C

Study Visit Day ± Visit Window	Screening ¹ (up to Day -28)	W1			W2	W3	W4	W8	W12	W20	W24	W35	COVID-19 Test	Notes ¹³	
		Day -1	Day 1	Day 2											

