8.4.1. Time Period and Frequency for Collecting AE and SAE Information

- All AEs and SAEs will be collected from dose administration until Week 35 at the timepoints specified in the SoA (Section 1.3). However, any SAEs assessed as related to study participation (e.g., study intervention, protocol-mandated procedures, invasive tests, or change in existing therapy) or related to a GSK product will be recorded from the time a participant consents to participate in the study.
- Medical occurrences that begin before the start of study intervention but after obtaining informed consent will be recorded as medical history/current medical conditions not as AEs.
- All SAEs will be recorded and reported to GSK immediately and under no circumstance should this exceed 24 hours, as indicated in Section 10.3. The investigator will submit any updated SAE data to GSK within 24 hours of it being available.
- Investigators are not obligated to actively seek information on AEs or SAEs after conclusion of the study participation. However, if the investigator learns of any SAE, including a death, at any time after a participant has been discharged from the study, and he/she considers the event to be reasonably related to the study intervention or study participation, the investigator must promptly notify GSK.

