4.2.2.3. Main Analytical Approach

The analyses described in the following sections, will be performed using the Safety analysis set in all study parts, as defined in Section 3. Unless otherwise specified, available data will be analyzed as collected regardless of intercurrent events that may occur (treatment policy). Missing data will not be imputed.

Incidence of AEs, SAEs, and AESIs through Day 29 will be displayed in the form of summaries and listings, where appropriate. Further details are provided below.

Adverse Events

Adverse events will be coded using Medical Dictionary for Regulatory Activities (MedDRA) central coding dictionary. Adverse events analyses including the analysis of AEs, SAEs and other significant AEs will be based on GSK Core Data Standards.

Adverse event displays to be generated include: overview of AEs, all AEs, all SAEs, AEs leading to permanent discontinuation of study treatment or permanent withdrawal from study, common ($\geq 5\%$) AEs, common ($\geq 5\%$) Non-Serious AEs, common ($\geq 5\%$) SAEs, Drug-related AEs, Serious Drug-related AEs, Non-Serious Drug-related AEs, and Adverse events leading to withdrawal. For Part C, common ($\geq 1\%$) AEs, common ($\geq 1\%$) Non-Serious AEs, common ($\geq 1\%$) SAEs may be additionally reported. The number and percentages of participants with the event will be summarized by System Order Class (SOC) and Preferred Term (PT), unless otherwise specified in the [OPS](#). Adverse Events including fatal SAEs and AEs leading to withdrawal will also be listed as specified in the [OPS](#).

A drug-related AE is defined as an AE for which the investigator classifies the relationship to study intervention as “Yes”. A worst-case scenario approach will be taken to handle missing relatedness data, i.e. the summary table will include events with the relationship to study intervention as ‘Yes’ or missing.

Adverse Events of Special Interest

Adverse events of special interest will be monitored by GSK at Day 29 and either during or at the end of the study (through Week 35). These will be updated during the course of the study based on accumulating safety data.

Adverse event of special interest includes:

- Hypersensitivity reactions occurring any time post dose

- Infusion-related reactions within 24 hours post dose (Part C)
- Injection site reactions (Part A)
- Immunogenicity
- AEs potentially related to antibody-dependent enhancement of disease

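### Investigator withdrawal after the single dose can only cut safety follow-up short; keeping the Week 35 telephone contact for these participants would be a cheap improvement

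*Protocol*

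**What the plan says.** Protocol Section 7.2 covers leaving the study. Besides withdrawing at their own request, a participant "may be withdrawn at any time at the discretion of the investigator for safety, behavioral, or compliance reasons". The section adds: "This is expected to be uncommon". On the consequence it says: "The participant will be permanently discontinued from the study intervention and the study at that time". It also provides an exit visit: "At the time of discontinuing from the study, if possible, an early discontinuation visit should be conducted, as shown in the SoA".

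Protocol Section 7.1 covers a dose stopped part-way. There, "the participant will remain in the study to be evaluated for follow-up safety assessments as indicated in the SoA".

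On collection, Protocol Section 8.4.1 states: "All AEs and SAEs will be collected from dose administration until Week 35". The same section releases investigators from any duty to look for further events once participation has ended, although a related SAE that comes to their notice later must still be reported.

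The Part A and B Schedule of Activities (Protocol Section 1.3, note 16) says: "If participant withdraws early from the study prior to Week 24, then the W24 visit assessments will be performed as the ED/EW visit". For exits after Week 24, the Week 35 assessments are done at the exit visit. The wording of the corresponding Part C note is not visible in the text available for this review.

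For the analysis, SAP Section 4.2.2.3 says "available data will be analyzed as collected regardless of intercurrent events that may occur (treatment policy). Missing data will not be imputed". Membership of the Safety set (SAP Section 3) depends on exposure, not on completing follow-up.

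**The concern.** A single-dose trial gains nothing in drug exposure by taking a fully dosed participant out of the study. The protocol follows this reasoning in Section 7.1.1, where individual liver stopping criteria are set aside because there is only one dose. Section 7.2 does not follow it.

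Incidence of AEs, SAEs and AEs of special interest (AESIs) through Day 29 is a primary endpoint in Parts A and C, under a treatment-policy strategy whose only named intercurrent event is an incomplete dose. Withdrawal from the study simply produces missing data. Because the participant stays in the denominator, an event that starts after exit and is never learned of is counted as absent.

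Two outcomes are exposed:

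- **The primary Day 29 safety endpoint**, by exits before Day 29.
- **The Week 35 safety endpoint and the watch for antibody-dependent enhancement**, by any exit before Week 35. Protocol Sections 2.3.1 and 8.4.7.4 rely on about five half-lives of follow-up to look for enhanced disease as drug levels wane.

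**Working it through.** **1. What withdrawal removes, by case**

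- *The event that prompted withdrawal:* kept. Section 8.4 leaves the investigator responsible for following AEs that are serious, related, or the cause of leaving the study.
- *SAEs and AESIs already reported:* kept. Section 8.4.3 follows them to resolution, stabilization, another explanation or loss to follow-up.
- *New events up to the exit visit:* kept, if that visit takes place.
- *New events after exit:* not actively sought (Section 8.4.1).
- *Week 35 contact, Parts A and B:* none specified after an exit before Week 24. After Week 24 it is brought forward, so events between that contact and Week 35 are not sought.
- *Week 35 contact, Part C:* cannot be read from the available note. For Part C the point rests on Sections 7.2 and 8.4.1.

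**2. Timing against the enhancement watch**

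The Amendment 1 rationale (Protocol Section 10.9) gives a half-life of about 48.8 days. 5 × 48.8 = 244 days, and Week 35 is 35 × 7 = 245 days. An exit visit at Day 29 (28 days after dosing) is at 28/48.8 ≈ 0.6 half-lives. The Week 24 visit (Day 168) is at about 168/48.8 ≈ 3.4. An exit visit before Week 24 therefore cannot stand in for the late contact.

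**3. The plan's own safety figure**

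Protocol Section 9.5 gives a 90% chance of seeing at least one event among 200 at a true rate of 1.14%. Check: 1 − (1 − 0.0114)^200 = 0.899. It reproduces. The 1.14% is the infusion-related reaction rate in an earlier trial, and such reactions are defined here as occurring within 24 hours of dosing (Section 8.4.7). Later withdrawal cannot hide them, so this figure is left alone.

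**4. Illustration for a late event with none observed**

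The exact two-sided 95% upper limit for 0/n is 1 − 0.025^(1/n). The documents give no withdrawal rate, so the losses below are assumptions.

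| Group | Observed to Week 35 | Upper limit |
|---|---|---|
| Part C Cohort 1, none lost | 200 | 1.83% |
| 1% lost | 198 | 1.85% |
| 2% lost | 196 | 1.86% |
| 5% lost | 190 | 1.92% |
| 10% lost | 180 | 2.03% |
| Part A dorsogluteal arm, none lost | 63 | 5.69% |
| One lost | 62 | 5.78% |
| Part A thigh or deltoid arm, none lost | 32 | 10.89% |
| One lost | 31 | 11.22% |

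**5. Worst case for a commoner event**

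Suppose 10 of 200 have the event (5.0%) and every withdrawn participant had it unseen. With 2 withdrawn the incidence is 12/200 = 6.0%, with 4 it is 14/200 = 7.0%, and with 10 it is 20/200 = 10.0%. These are outer bounds. Only frequent, strongly outcome-related withdrawal would bring the true figure near them.

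**The case against.** The strongest reply is that the plan already contains most of the protection needed. There is an exit visit, Section 7.2 points to the Schedule of Activities for further evaluations, and reported events of concern are followed. Pregnancies are to be collected to Week 35 (Section 8.4.5). The SAP summarizes withdrawal reasons and outcomes of AEs leading to withdrawal (Section 6.1.1) and time on study after dosing (Section 6.1.2). Someone withdrawn for a safety event is normally already counted in the any-AE row. All of this stands, and it limits the loss to new events starting after exit.

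A reader might infer four stronger things that the documents do not support:

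- **That withdrawal ends AE collection altogether.** It ends the active search for new events; the provisions above remain.
- **That safety data are lost selectively.** A safety-triggered exit could be related to outcome, but nothing in the documents shows that it would be, and no rate is given. The 20% allowance in Section 9.5 is for PK non-evaluability in Parts A and B and is not a withdrawal rate.
- **That the 90% detection statement is eroded.** Its rate belongs to reactions within 24 hours of dosing.
- **That Sections 7.1 and 7.2 contradict each other.** One governs stopping a dose and the other leaving the study. Section 7.2 has no exception for partly dosed participants, so they too could be withdrawn.

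The reply does not cover the missing Week 35 contact after a Part A or B exit before Week 24.

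**Conclusion.** The point holds as a cheap improvement. For a fully dosed participant, investigator withdrawal serves only to end follow-up. That fits poorly with a treatment-policy safety endpoint, a collection window to Week 35 and a late watch for enhanced disease. Any bias is towards lower incidence, because unseen later events are counted as non-events in a denominator defined by dosing.

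The size is probably small. At assumed losses of 1% to 5% in Part C Cohort 1, the upper limit for an unseen late event moves by less than 0.1 percentage point (1.83% to 1.92% at most). Even the 10% row covers more exits than the change would reach, since only investigator decisions are affected and participants may still refuse contact. No stated sample-size or precision figure needs correcting.

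This rests on two assumptions: that withdrawal is uncommon, as the protocol expects, and that the unread Part C note does not already provide a Week 35 contact. If it does, the Part C half of the point largely falls away.

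**What to change.** Reconcile Protocol Sections 7.1, 7.2 and 8.4.1 with the early-withdrawal notes in the Schedule of Activities (note 16 for Parts A and B and its Part C counterpart). State that once any study intervention has been given, an investigator's decision to withdraw a participant ends on-site procedures only. Collection of AEs, SAEs, AESIs, concomitant medication and pregnancy then continues by telephone at Day 29, if not yet reached, and at Week 35, unless the participant withdraws consent to contact. The notes should say that the exit visit does not replace the Week 35 call for these participants. The participant's own right to withdraw is unchanged.

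Optionally, footnote the number followed to Week 35 by arm in the Week 35 AE tables. This adds little, because time on study and withdrawal reasons are already summarized.

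The cost is protocol wording and one or two calls for a few participants, some of which will go unanswered. The Week 35 call already exists.
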